6.2 Rituximab

Rituximab (Rituxan®, MabThera®) is a genetically engineered chimeric murine/human monoclonal immunoglobulin (Ig) G1 kappa antibody directed against the B cell specific CD20 antigen. In RA patients, treatment with rituximab induces depletion of peripheral B lymphocytes, with the majority of patients demonstrating near complete depletion (CD19 counts below the lower limit of quantification, 20 cells/µL) within 2 weeks after receiving the first dose. Most patients showed peripheral B cell depletion for at least 6 months. A small proportion of patients (~4%) had prolonged peripheral B cell depletion lasting more than 3 years after a single course of treatment ([Biogen Idec, 2013](#)).

Total serum Ig levels, IgM, IgG, and IgA were reduced at 6 months with the greatest change observed in IgM. In RA patients during repeated rituximab treatment, 23.3%,

5.5%, and 0.5% of patients experienced decreases in IgM, IgG, and IgA concentrations below the lower limit of normal, respectively, at any time after receiving rituximab. The clinical consequences of decreases in Ig levels in RA patients are unclear ([Biogen Idec, 2013](#)).

Treatment with rituximab in patients with RA is associated with reduction of certain biologic markers of inflammation such as interleukin (IL)-6, CRP, serum amyloid protein (SAA), S100 A8/S100 A9 heterodimer complex (S100 A8/9), anti-cyclic citrullinated peptide (anti-CCP), and rheumatoid factor (RF; [Biogen Idec, 2013](#)).

Rituximab is indicated, in combination with methotrexate (MTX), for the treatment of adult patients with moderately- to severely-active RA who have had an inadequate response to one or more tumor necrosis factor (TNF) antagonist therapies. Rituximab is approved for use in other indications such as non-Hodgkin lymphoma, chronic lymphocytic leukemia, granulomatosis with polyangiitis, and microscopic polyangiitis ([Biogen Idec, 2013](#)).

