11.1.2 Reporting Procedures for Adverse Events

The Investigator is responsible for ensuring that all AEs observed by the Investigator or reported by the subject that occur from the day of randomization until the week 48 visit (or through 28 days after the last dose of investigational product for subjects who discontinue study early) are reported using the applicable eCRF Adverse Event Summary page. AEs observed by the Investigator or reported by the subject that occur after signing of informed consent but before randomization will be recorded.

The Investigator must assign the following AE attributes:

- AE diagnosis or syndrome(s), if known (if not known, signs or symptoms)
- dates of onset and resolution
- severity
- assessment of relatedness to IP
- action taken

AEs must be graded for severity according to the National Cancer Institute (US) Common Terminology Criteria for Adverse Events (CTCAE) version 4.03 (http://ctep.cancer.gov/protocolDevelopment/electronic_applications/ctc.htm).

The Investigator must assess whether the AE is possibly related to the investigational product. This relationship is indicated by a "yes" or "no" response to the question: "Is

there a reasonable possibility that the event may have been caused by the investigational product?"

The Investigator is responsible for reviewing laboratory test results and determining whether an abnormal value in an individual study subject represents a clinically significant change from the subject's baseline values. In general, abnormal laboratory findings without clinical significance (based on the Investigator's judgment) are not to be recorded as AEs. However, laboratory value changes that require treatment or adjustment in current therapy are considered AEs. Where applicable, clinical sequelae (not the laboratory abnormality) are to be recorded as the AE.

The Investigator's clinical judgment is used to determine whether a subject is to be removed from treatment due to an AE. A subject, or subject's legal guardian, can also voluntarily withdraw from treatment due to an AE. If the subject withdraws consent, the subject is encouraged to undergo, at a minimum, an EOS assessment.

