## 5.4 SAFETY

### Adverse Event of Interest (AEOI)

An AEOI is defined as a noteworthy TEAE for a particular product or class of products that a sponsor may wish to monitor carefully. It could be serious or non-serious, and could include events that might be potential precursors or prodromes for more serious medical conditions in susceptible individuals (Council for International Organizations of Medical Sciences [CIOMS] VI, 2005). The AEOIs for this study will include:

- infusion reactions including hypersensitivity,
- cardiac disorders,
- serious infections,
- progressive multifocal leukoencephalopathy,
- hematological reactions,
- hepatitis B reaction,
- opportunistic infections
- hypogammaglobulinemia.
- severe mucocutaneous reactions,
- gastrointestinal perforation

Events of interest were identified using the latest versions of pre-specified Standardised MeDRA query (SMQ) where available. If no SMQ is available for use as a search tool for a given EOI (eg. Infusion reactions), a customized search strategy developed at Amgen or medical review will be used where SMQ is not available. [Appendix 5](#) provides the search strategy used to retrieve the events of interest. The preferred terms used in the searches are stored in a central PRA server location for analyses.

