### 9.6.2 IgA, IgG and IgM

The total IgA, IgG and IgM levels as well as change from baseline will be summarized descriptively by treatment and visit.

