**APPENDIX 5 LIST OF EVENTS OF INTEREST AND THE ASSOCIATED SMQ AND EOI SEARCHING STRATEGIES**

Event of Interest	Category of EOI query (SMQ, Amgen query, or SOC)	Search Strategy	Additional Medical Review of the SMQ or SOC dataset for confirmation of the EOI
Infusion reactions including Hypersensitivity	Infusion reactions (Amgen query)	Broad*- TEAE with start date same as, or one day after, IP administration date	No
	Hypersensitivity (SMQ)	Broad- TEAE with start date same as, or one day after, IP administration date	No
Cardiac disorders	Cardiac disorders (SOC)		No
Serious infections	Infections and Infestations (SOC)	CTCAE grade >=3 or the serious TEAE	No
Progressive multifocal leukoencephalopathy	Progressive multifocal leukoencephalopathy (Amgen query)	Broad	Yes
Hematological reactions	Hematopoietic cytopenia (SMQ)	Broad	No
Hepatitis B reactivation	Hepatitis B Infection (Amgen query)	Broad	Yes
Opportunistic infections	Infections and infestations (SOC)		Yes
Hypogammaglobulinemia	Immune mediated events associated with oncologic immune therapies (Amgen query)	Broad	Yes

Sponsor: Amgen Inc.

Statistical Analysis Plan

Protocol No: 20130108

10-December-2018/ Version 2.0

Severe mucocutaneous reactions	Severe cutaneous adverse reactions (SMQ)	CTCAE grade >=3 or the serious TEAE, Broad search	No
Gastrointestinal perforation	Gastrointestinal perforation(SMQ)	Narrow	No

\*Broad search strategy includes both narrow scope terms and broad scope terms.

Sponsor: Amgen Inc.

Statistical Analysis Plan

Protocol No: 20130108

10-December-2018/ Version 2.0

---

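### Hypogammaglobulinemia is a named event of interest, but no listed output counts subjects whose measured IgG, IgA or IgM falls below the lower limit of normal, and the adverse-event search for it cannot be verified from the plan

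*SAP*

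**What the plan says.** **Event of interest.** The list in SAP 5.4 that opens with "The AEOIs for this study will include" includes hypogammaglobulinemia. Appendix 6 gives it two tables of its own (14-6.6.1.8.1 and 14-6.6.1.8.2), one for each safety period.

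**How it is found.** The Appendix 5 row assigns it to a sponsor query titled "Immune mediated events associated with oncologic immune therapies (Amgen query". The search is marked Broad, and a footnote explains: "Broad search strategy includes both narrow scope terms and broad scope terms". The row is also marked Yes in the column headed "Additional Medical Review of the SMQ or SOC dataset for confirmation of the EOI". The terms are not printed; SAP 5.4 says: "The preferred terms used in the searches are stored in a central PRA server location for analyses".

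**What is measured.** Protocol Table 1 schedules IgG, IgA and IgM at baseline, week 4, week 24 before the second dose, and week 48/EOS, with IgM also on days 2 and 3.

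**What is done with it.** SAP 9.6.2: "The total IgA, IgG and IgM levels as well as change from baseline will be summarized descriptively by treatment and visit". This sits under pharmacodynamics, on the full analysis set by randomized treatment. The laboratory groups in SAP 9.8.3, which feed the shift and grade 3 or higher tables, are hematology and serum chemistry only.

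**What sites report.** Protocol 11.1.2 says that in general "abnormal laboratory findings without clinical significance (based on the Investigator's judgment) are not to be recorded as AEs".

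**Background.** For repeated rituximab treatment in RA, Protocol 6.2 gives 23.3%, "5.5%, and 0.5% of patients experienced decreases in IgM, IgG, and IgA concentrations below the lower limit of normal", respectively, at any time after treatment.

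**The concern.** Two features combine. First, the title of the query names a different safety concept from the event it is meant to find. With the terms unprinted, a reader of the plan cannot tell whether it retrieves low-immunoglobulin terms. Second, the laboratory data that would show the risk directly are never turned into a count of subjects. Summary statistics by visit do not give the number of subjects who went below normal at any time.

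Safety compared with rituximab is a stated secondary objective. At stake is whether the report can compare this named risk between arms on the measure the protocol itself uses for rituximab. As planned, the dedicated tables rest on adverse events alone, and a reader may take a low count there as evidence about immunoglobulin lowering that those tables were not built to give.

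**Working it through.** The plan states no figure for this point, so there is none to reproduce. The check has two parts.

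**1. Trace a laboratory-only case through the planned outputs.** Take a subject whose IgM falls below the lower limit of normal and whose investigator judges this not clinically significant.

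- Adverse-event data: under Protocol 11.1.2 the finding is generally not recorded. It then cannot reach the hypogammaglobulinemia tables or the general preferred-term tables (14-6.2.2.1 and 14-6.2.2.2), whatever the query contains.
- Laboratory shift and grade 3 or higher tables (SAP 9.8.3; section 14.7 of Appendix 6): hematology and chemistry only.
- Pharmacodynamic table 14-11.1.1: the value enters a by-visit summary but is not counted as low.
- Listings 16-2.8.1 and 16-2.8.2: hematology and chemistry only. No listed subject listing shows immunoglobulins, so the count could not be rebuilt from listings.

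The subject is counted in no listed output.

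**2. Scale, if such subjects were counted.**

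Inputs: n = 100 per arm (SAP section 3) and the Protocol 6.2 rates p. The assumption is that rates seen at any time under repeated treatment carry over to two doses and 48 weeks.

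- Expected subjects = n × p
- Probability of at least one = 1 − (1 − p)^n
- 95% half-width of a risk difference, 100 vs 100, equal true rates = 1.96 × √(2p(1 − p)/100)

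| | p | Expected per 100 | P(at least one) | Half-width, 100 vs 100 |
|---|---|---|---|---|
| IgM | 0.233 | 23.3 | 1.00 | 1.96 × √(2 × 0.233 × 0.767/100) = 11.7 points |
| IgG | 0.055 | 5.5 | 0.997 | 1.96 × √(2 × 0.055 × 0.945/100) = 6.3 points |
| IgA | 0.005 | 0.5 | 0.39 | too few events for this formula to be useful |

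Range on the assumption:

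- With 85 subjects per arm (the plan's 15% dropout by week 24), the expected counts are 85 × p = 19.8, 4.7 and 0.4.
- With half the cited rates and 100 per arm, they are 11.7, 2.8 and 0.3.

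**Share captured by the adverse-event search.** This cannot be computed, because neither the query terms nor the rate at which sites would report low immunoglobulin is in the documents. Across the whole possible range, the number per 100 subjects that would surface as events of interest is:

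| Assumed capture | 0% | 10% | 25% | 50% | 75% | 100% |
|---|---|---|---|---|---|---|
| IgM | 0 | 2.3 | 5.8 | 11.7 | 17.5 | 23.3 |
| IgG | 0 | 0.6 | 1.4 | 2.8 | 4.1 | 5.5 |

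**The case against.** A reader might infer that the risk would be largely missed and that the dedicated tables would show close to zero events. The documents do not support that.

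- The query's contents are unseen and may include the right terms. The search is Broad and followed by medical review. Opportunistic infections are handled in a similar way, by a wide net (a whole system organ class) and then review.
- Protocol 11.1.2 also makes laboratory changes that need treatment or a change in therapy adverse events, and Protocol 10.8 says clinically relevant changes are reported. SAP 9.8.1 tabulates every treatment-emergent event by preferred term, so a reported case appears by arm even if the query misses it.
- SAP 5.4 defines an event of interest as a noteworthy adverse event, not a laboratory threshold. Protocol 6.2 calls the clinical consequences of lowered immunoglobulin in RA unclear.
- Under SAP section 9 the by-visit summaries include the median, quartiles, minimum and maximum, so a clear difference between arms could be visible.
- The table shells are a separate document, and a below-limit count there cannot be ruled out.

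Most of this stands, and it limits the point to cases seen only in laboratory values. It does not remove the point. As its column heading describes it, medical review confirms retrieved events and does not add others. The general tables hold only what sites report. Quartiles and extremes at each visit do not give the number of subjects ever below the limit. No listed title suggests that the shells contain such a count. The comparison would also be imprecise: for IgG the 6.3-point half-width exceeds the 5.5% rate. The count would still be informative as a description.

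**Conclusion.** The laboratory part holds on the documents: no listed output counts subjects with immunoglobulin below the lower limit of normal, and those whose low values are judged not clinically significant generally do not enter the adverse-event tables either. If the Protocol 6.2 rates carried over, that measure would apply to about 23 subjects per 100 for IgM, 5 to 6 for IgG and 0 to 1 for IgA. Those figures include any subjects also reported as adverse events, and they may be too high for two doses with three scheduled post-baseline IgG and IgA samples.

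The query part holds only as a matter of verification: the title does not name the event and the terms are not given, so the adequacy of the search cannot be judged either way. This is a worthwhile, inexpensive improvement. It does not show that the risk goes unmeasured.

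**What to change.** **SAP 9.6.2 and 9.8.3.** Add, on the Safety Analysis Set by actual treatment and for both safety periods of SAP 9.8, the number and percent of subjects with any post-baseline value below the lower limit of normal, among those not below it at baseline. Do this for IgG, IgM and IgA separately.

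- Name the reference range to be used, and state that the week 24 sample drawn before the second dose belongs to the first period.
- Give the risk difference and 95% CI for ABP 798 against each rituximab arm, as SAP 9.8.1 already does for events of interest.
- Do not pool the rituximab arms for the entire-study period. The US arm switches to ABP 798 for the second dose, so only the EU arm stays on rituximab throughout.

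**SAP Appendix 5.** Confirm that the query contains the low-immunoglobulin preferred terms (hypogammaglobulinaemia, decreased blood immunoglobulin G, A or M, and similar), and add them if it does not. Replacing the query unseen is not justified.

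**Cost.** One or two extra tables from data already collected, with no new sample or visit. The downside is a higher reported incidence of this risk, which the report should present as a laboratory finding alongside the adverse-event count.

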## APPENDIX 6 LIST OF POST-TEXT TABLES, FIGURES, LISTINGS, AND SUPPORTIVE SAS OUTPUT APPENDICES

Table Number	Table Title
14.1	Disposition and Analyzed Dataset Tables
Table 14.1.1	Subject Analysis Sets by Treatment (All Screened Subjects)
Table 14-1.2.1.	Randomization by Region, Country and Center (Full Analysis Set)
Table 14-1.2.2.	Randomization by Stratification Factors (Full Analysis Set)
Table 14-1.3.1.	Subject Study Disposition by Treatment (Full Analysis Set)
Table 14-1.3.2.	Subject Study Disposition by Treatment (Safety Analysis Set)
Table 14-1.3.3.	Subject Study Disposition by Treatment (Pharmacokinetic Concentration Analysis Set)
Table 14-1.3.4.	Subject Study Disposition by Treatment (Pharmacokinetic Parameter Analysis Set)
Table 14-1.3.5.	Subject Study Disposition by Treatment (Per Protocol Analysis Set)
Table 14-1.3.6.	Subject Study Disposition by Treatment (Per Protocol Pharmacokinetic Parameter Analysis Set)
Table 14-1.3.7.	Subject Study Disposition by Treatment (Anti-drug Antibody Analysis Set)
14.2	Demographic and Baseline Characteristics Data Tables
Table 14-2.1.	Demographic and Baseline Characteristics by Treatment (Full Analysis Set)
Table 14-2.2.	Demographic and Baseline Characteristics by Treatment (Safety Analysis Set)
Table 14-2.3.	Demographic and Baseline Characteristics by Treatment (Pharmacokinetic Concentration Analysis Set)
Table 14-2.4.	Demographic and Baseline Characteristics by Treatment (Pharmacokinetic Parameter Analysis Set)
Table 14-2.5.	Demographic and Baseline Characteristics by Treatment (Per Protocol Analysis Set)

Sponsor: Amgen Inc.

Statistical Analysis Plan

Protocol No: 20130108

10-December-2018/ Version 2.0

---

Table 14-2.6.	Demographic and Baseline Characteristics by Treatment (Per Protocol Pharmacokinetic Parameter Analysis Set)
Table 14-2.7.	Demographic and Baseline Characteristics by Treatment (Anti-drug Antibody Analysis Set)
Table 14-2.8.1.	Resolved Medical Conditions at Randomization by System Organ Class, Preferred Term, and Treatment (Safety Analysis Set)
Table 14-2.8.2.	Unresolved Medical Conditions at Randomization by System Organ Class, Preferred Term, and Treatment (Safety Analysis Set)
Table 14-2.9.	Prior Medications by Preferred Name and Treatment (Safety Analysis Set)

**14.3 Measures of Treatment Compliance Data Tables**

Table 14-3.1.	Inclusion/Exclusion Criteria Protocol Deviations (Full Analysis Set)
Table 14-3.2.	Important Protocol Deviations (Full Analysis Set)
Table 14-3.3.	Concomitant Medications by Preferred Name and Treatment (Safety Analysis Set)

**14.4 Efficacy Data Tables**

Table 14-4.1.1.	Repeated Measures Analysis of DAS28-CRP Change From Baseline at Week 24 – Primary Analysis (Full Analysis Set)
Table 14-4.1.2.	Analysis of DAS28-CRP Change From Baseline at Week 24 – Sensitivity Analysis (Full Analysis Set)
Table 14-4.1.3.1.	Repeated Measures Analysis of DAS28-CRP Change From Baseline by Visit – Day 1 Through Week 24 (Full Analysis Set)
Table 14-4.1.3.2.	Repeated Measures Analysis of DAS28-CRP Change From Baseline by Visit – Day 1 Through Week 24 (Per Protocol Analysis Set)
Table 14-4.1.4.1.	Analysis of DAS28-CRP Change From Baseline by Visit – Day 1 Through End of Study (Full Analysis Set)
Table 14-4.1.4.2.	Analysis of DAS28-CRP Change From Baseline by Visit – Day 1 Through End of Study (Full Analysis Set – Subgroup who received the 1st infusion of the 2nd dose at week 24 )
Table 14-4.1.5.	Summary for Reason of Missing DAS28-CRP Change from Baseline Results at Week 24 (Full Analysis Set)
Table 14-4.1.6.	Tipping Point Analysis Results for Mean Difference of DAS28-CRP Change From Baseline at Week 24 for ABP 798 vs Rituximab with 90% Confidence Interval (Full Analysis Set)

Sponsor: Amgen Inc.

Statistical Analysis Plan

Protocol No: 20130108

10-December-2018/ Version 2.0

Table 14-4.1.7.	Repeated Measures Analysis with Additional Selective Covariates for DAS28-CRP Change From Baseline at Week 24 (Full Analysis Set)
Table 14-4.2.1.	Repeated Measures Analysis of DAS28-CRP Change From Baseline by Age Subgroup - Day 1 Through Week 24 (Full Analysis Set)
Table 14-4.2.2.	Repeated Measures Analysis of DAS28-CRP Change From Baseline by Race Subgroup – Day 1 Through Week 24 (Full Analysis Set)
Table 14-4.2.3.	Repeated Measures Analysis of DAS28-CRP Change From Baseline by Gender Subgroup – Day 1 Through Week 24 (Full Analysis Set)
Table 14-4.2.5.	Repeated Measures Analysis of DAS28-CRP Change From Baseline by Binding Anti-drug Antibodies Status Subgroup – Day 1 Through Week 24 (Full Analysis Set)
Table 14-4.2.6.	Repeated Measures Analysis of DAS28-CRP Change From Baseline by Neutralizing Anti-drug Antibodies Status Subgroup – Day 1 Through Week 24 (Full Analysis Set)
Table 14-4.2.7.	Repeated Measures Analysis of DAS28-CRP Change From Baseline by Baseline Oral Corticosteroid Use Subgroup – Day 1 Through Week 24 (Full Analysis Set)
Table 14-4.3.1.	Repeated Measures Analysis of DAS28-CRP Change From Baseline by Geographic Region Subgroup – Day 1 Through Week 24 (Full Analysis Set)
Table 14-4.3.2.	Repeated Measures Analysis of DAS28-CRP Change From Baseline by Seropositivity Subgroup – Day 1 Through Week 24 (Full Analysis Set)
Table 14-4.3.3.	Repeated Measures Analysis of DAS28-CRP Change From Baseline by Prior Biologics Use Subgroup – Day 1 Through Week 24 (Full Analysis Set)
Table 14-4.5.1.1	Repeated Measures Analysis of ACR20 by Visit – Day 1 Through Week 24 (Full Analysis Set)
Table 14-4.5.1.2	Repeated Measures Analysis of ACR20 by Visit – Day 1 Through Week 24 (Per Protocol Analysis Set)
Table 14-4.5.2.1.	Analysis of ACR20 by Visit – Day 1 Through End of Study (Full Analysis Set)

Sponsor: Amgen Inc.

Statistical Analysis Plan

Protocol No: 20130108

10-December-2018/ Version 2.0

Table 14-4.5.2.2.	Analysis of ACR20 by Visit – Day 1 Through End of Study (Full Analysis Set – Subgroup who received the 1st infusion of the 2nd dose at week 24)
Table 14-4.5.3.1	Repeated Measures Analysis of Hybrid ACR by Visit – Day 1 Through Week 24 (Full Analysis Set)
Table 14-4.5.3.2	Repeated Measures Analysis of Hybrid ACR by Visit – Day 1 Through Week 24 (Per Protocol Analysis Set)
Table 14-4.5.3.3.	Analysis of Hybrid ACR by Visit – Day 1 Through End of Study (Full Analysis Set)
Table 14-4.5.3.4.	Analysis of Hybrid ACR by Visit – Day 1 Through End of Study (Full Analysis Set – Subgroup who received the 1st infusion of the 2nd dose at week 24)
Table 14-4.6.1.	Repeated Measures Analysis of ACR50 by Visit – Day 1 Through Week 24 (Full Analysis Set)
Table 14-4.6.2.1.	Analysis of ACR50 by Visit – Day 1 Through End of Study (Full Analysis Set)
Table 14-4.6.2.2.	Analysis of ACR50 by Visit – Day 1 Through End of Study (Full Analysis Set – Subgroup who received the 1st infusion of the 2nd dose at week 24)
Table 14-4.7.1.	Repeated Measures Analysis of ACR70 by Visit – Day 1 Through Week 24 (Full Analysis Set)
Table 14-4.7.2.1.	Analysis of ACR70 by Visit – Day 1 Through End of Study (Full Analysis Set)
Table 14-4.7.2.2.	Analysis of ACR70 by Visit – Day 1 Through End of Study (Full Analysis Set – Subgroup who received the 1st infusion of the 2nd dose at week 24 )
Table 14-4.8.1.	Summary of Swollen Joint Counts by Visit (Full Analysis Set)
Table 14-4.8.2.	Summary of Tender Joint Counts by Visit (Full Analysis Set)
Table 14-4.8.3.	Summary of Subject's Global Health Assessment by Visit (Full Analysis Set)
Table 14-4.8.4.	Summary of Investigator's Global Health Assessment by Visit (Full Analysis Set)
Table 14-4.8.5.	Summary of Subject's Assessment of Disease-related Pain by Visit (Full Analysis Set)
Table 14-4.8.6.	Summary of HAQ-DI Total Score by Visit (Full Analysis Set)
Table 14-4.8.7.	Summary of CRP by Visit (Full Analysis Set)

Sponsor: Amgen Inc.

Statistical Analysis Plan

Protocol No: 20130108

10-December-2018/ Version 2.0

Table 14-4.8.8.	Summary of Swollen Joint Counts by Visit – DAS28-CRP Component (Full Analysis Set)
Table 14-4.8.9.	Summary of Tender Joint Counts by Visit – DAS28-CRP Component (Full Analysis Set)
Table 14-4.8.10.	Summary of Subject's Global Health Assessment by Visit – DAS28-CRP Component (Full Analysis Set)
Table 14-4.8.11.	Summary of CRP by Visit – DAS28-CRP Component (Full Analysis Set)
Table 14-4.10.1.1.	Repeated Measures Analysis of DAS28-CRP Change From Baseline at Week 24 Comparing ABP 798 with Pooled Rituximab (Full Analysis Set)
Table 14-4.10.1.2.	Analysis of DAS28-CRP Change From Baseline (ANCOVA) at Week 24 Comparing ABP 798 with Pooled Rituximab (Full Analysis Set)
Table 14-4.10.1.3.1.	Repeated Measures Analysis of DAS28-CRP Change From Baseline Comparing ABP 798 with Pooled Rituximab by Visit – Day 1 Through Week 24 (Full Analysis Set)
Table 14-4.10.1.3.2.	Repeated Measures Analysis of DAS28-CRP Change From Baseline Comparing ABP 798 with Pooled Rituximab by Visit – Day 1 Through Week 24 (Per Protocol Analysis Set)
Table 14-4.10.1.4.1.	Analysis of DAS28-CRP Change From Baseline (ANCOVA) Comparing ABP 798 with Pooled Rituximab by Visit – Day 1 Through End of Study (Full Analysis Set)
Table 14-4.10.1.4.2.	Analysis of DAS28-CRP Change From Baseline (ANCOVA) Comparing ABP 798 with Pooled Rituximab by Visit – Day 1 Through End of Study (Per Protocol Set)
Table 14-4.10.1.6.	Tipping Point Analysis Results for Mean Difference of DAS28-CRP Change From Baseline at Week 24 for ABP 798 vs Pooled Rituximab with 90% Confidence Interval (Full Analysis Set)
Table 14-4.10.1.7.	Repeated Measures Analysis with Additional Selective Covariates for DAS28-CRP Change From Baseline at Week 24 Comparing ABP 798 with Pooled Rituximab (Full Analysis Set)
Table 14-4.10.5.1	Repeated Measures Analysis of DAS28-CRP Change From Baseline Comparing ABP 798 with Pooled Rituximab by Age Subgroup - Day 1 Through Week 24 (Full Analysis Set)
Table 14-4.10.5.2	Repeated Measures Analysis of DAS28-CRP Change From Baseline Comparing ABP 798 with Pooled Rituximab by Race Subgroup – Day 1 Through Week 24 (Full Analysis Set)

Sponsor: Amgen Inc.

Statistical Analysis Plan

Protocol No: 20130108

10-December-2018/ Version 2.0

Table 14-4.10.5.3	Repeated Measures Analysis of DAS28-CRP Change From Baseline Comparing ABP 798 with Pooled Rituximab by Gender Subgroup – Day 1 Through Week 24 (Full Analysis Set)
Table 14-4.10.5.5	Repeated Measures Analysis of DAS28-CRP Change From Baseline Comparing ABP 798 with Pooled Rituximab by Binding Anti-drug Antibodies Status Subgroup – Day 1 Through Week 24 (Full Analysis Set)
Table 14-4.10.5.6	Repeated Measures Analysis of DAS28-CRP Change From Baseline Comparing ABP 798 with Pooled Rituximab by Neutralizing Anti-drug Antibodies Status Subgroup – Day 1 Through Week 24 (Full Analysis Set)
Table 14-4.10.5.7	Repeated Measures Analysis of DAS28-CRP Change From Baseline Comparing ABP 798 with Pooled Rituximab by Baseline Oral Corticosteroid Use Subgroup – Day 1 Through Week 24 (Full Analysis Set)
Table 14-4.10.6.1	Repeated Measures Analysis of DAS28-CRP Change From Baseline Comparing ABP 798 with Pooled Rituximab by Geographic Region Subgroup – Day 1 Through Week 24 (Full Analysis Set)
Table 14-4.10.6.2	Repeated Measures Analysis of DAS28-CRP Change From Baseline Comparing ABP 798 with Pooled Rituximab by Seropositivity Subgroup – Day 1 Through Week 24 (Full Analysis Set)
Table 14-4.10.6.3	Repeated Measures Analysis of DAS28-CRP Change From Baseline Comparing ABP 798 with Pooled Rituximab by Prior Biologics Use Subgroup – Day 1 Through Week 24 (Full Analysis Set)
Table 14-4.11.5.1.1	Repeated Measures Analysis of ACR20 Comparing ABP 798 with Pooled Rituximab by Visit – Day 1 Through Week 24 (Full Analysis Set)
Table 14-4.11.5.1.2	Repeated Measures Analysis of ACR20 Comparing ABP 798 with Pooled Rituximab by Visit – Day 1 Through Week 24 (Per Protocol Analysis Set)
Table 14-4.12.1.1	Repeated Measures Analysis of Hybrid ACR Comparing ABP 798 with Pooled Rituximab by Visit – Day 1 Through Week 24 (Full Analysis Set)
Table 14-4.12.1.2	Repeated Measures Analysis of Hybrid ACR Comparing ABP 798 with Pooled Rituximab by Visit – Day 1 Through Week 24 (Per Protocol Analysis Set)

Sponsor: Amgen Inc.

Statistical Analysis Plan

Protocol No: 20130108

10-December-2018/ Version 2.0

---

Table 14-4.13.1	Repeated Measures Analysis of ACR 50 Comparing ABP 798 with Pooled Rituximab by Visit – Day 1 Through Week 24 (Full Analysis Set)
Table 14-4.14.1	Repeated Measures Analysis of ACR 70 Comparing ABP 798 with Pooled Rituximab by Visit – Day 1 Through Week 24 (Full Analysis Set)
Figure 14-4.10.	Mean DAS28-CRP Change from Baseline – Day 1 Through Week 24 (Full Analysis Set)
Figure 14-4.11.1.	Percent of Subjects Achieving ACR20 Response – Day 1 Through End of Study (Full Analysis Set)
Figure 14-4.11.2.	Percent of Subjects Achieving ACR50 Response – Day 1 Through End of Study (Full Analysis Set)
Figure 14-4.11.3.	Percent of Subjects Achieving ACR70 Response – Day 1 Through End of Study (Full Analysis Set)
Figure 14-4.11.4.	Mean Hybrid ACR – Day 1 Through End of Study (Full Analysis Set)
Figure 14-4.11.	ACR Response at Week 24 (Full Analysis Set)
Figure 14-4.12.	Mean DAS28-CRP Change from Baseline with Pooled Rituximab – Day 1 Through Week 24 (Full Analysis Set)
Figure 14-4.13.1.	Percent of Subjects Achieving ACR20 Response with Pooled Rituximab – Day 1 Through Week 24 (Full Analysis Set)
Figure 14-4.13.2.	Percent of Subjects Achieving ACR50 Response with Pooled Rituximab – Day 1 Through Week 24 (Full Analysis Set)
Figure 14-4.13.3.	Percent of Subjects Achieving ACR70 Response with Pooled Rituximab – Day 1 Through Week 24 (Full Analysis Set)
Figure 14-4.13.4.	Mean Hybrid ACR with Pooled Rituximab – Day 1 Through Week 24 (Full Analysis Set)
14.5	Extent of Exposure Tables
Table 14-5.1.	Investigational Product Exposure Summary by Treatment (Safety Analysis Set)
Table 14-5.2.	Investigational Product Administration by Visit and Treatment (Safety Analysis Set)
14.6	Adverse Events Data Tables
Table 14-6.1.1.	Overall Summary of Treatment-emergent Adverse Events by Treatment – Day 1 Until 1st Infusion of 2nd Dose (Safety Analysis Set)

Sponsor: Amgen Inc.

Statistical Analysis Plan

Protocol No: 20130108

10-December-2018/ Version 2.0

Table 14-6.1.2.	Overall Summary of Treatment-emergent Adverse Events by Treatment –Day 1 Through End of Study (Safety Analysis Set)
Table 14-6.2.1.1.	Treatment-emergent Adverse Events by System Organ Class, Preferred Term, and Treatment – Day 1 Until 1st Infusion of 2nd Dose (Safety Analysis Set)
Table 14-6.2.1.2.	Treatment-emergent Adverse Events by System Organ Class, Preferred Term, and Treatment – Day 1 Through End of Study (Safety Analysis Set)
Table 14-6.2.2.1.	Treatment-emergent Adverse Events by Preferred Term and Treatment – Day 1 Until 1st Infusion of 2nd Dose (Safety Analysis Set)
Table 14-6.2.2.2.	Treatment-emergent Adverse Events by Preferred Term and Treatment – Day 1 Through End of Study (Safety Analysis Set)
Table 14-6.2.2.3.	Treatment-emergent Adverse Events by Age Subgroup, Preferred Term and Treatment – Day 1 Until 1st Infusion of 2nd Dose (Safety Analysis Set)
Table 14-6.2.2.4.	Treatment-emergent Adverse Events by Age Subgroup, Preferred Term and Treatment – Day 1 Through End of Study (Safety Analysis Set)
Table 14-6.2.3.1.	Treatment-emergent Adverse Events by System Organ Class, Preferred Term, Maximum CTCAE Grade, and Treatment – Day 1 Until 1st Infusion of 2nd Dose (Safety Analysis Set)
Table 14-6.2.3.2.	Treatment-emergent Adverse Events by System Organ Class, Preferred Term, Maximum CTCAE Grade, and Treatment – Day 1 Through End of Study (Safety Analysis Set)
Table 14-6.2.4.1.	Grade $\geq 3$ Treatment-emergent Adverse Events by Preferred Term and Treatment - Day 1 Until 1st Infusion of 2nd Dose (Safety Analysis Set)
Table 14-6.2.4.2.	Grade $\geq 3$ Treatment-emergent Adverse Events by Preferred Term and Treatment – Day 1 Through End of Study (Safety Analysis Set)
Table 14-6.3.1.1.	Treatment-emergent Adverse Events Leading to Discontinuation of IP/Study by Preferred Term and Treatment – Day 1 Until 1st Infusion of 2nd Dose (Safety Analysis Set)
Table 14-6.3.1.2.	Treatment-emergent Adverse Events Leading to Discontinuation of IP/Study by Preferred Term and Treatment – Day 1 Through End of Study (Safety Analysis Set)

Sponsor: Amgen Inc.

Statistical Analysis Plan

Protocol No: 20130108

10-December-2018/ Version 2.0

---

Table 14-6.3.1.3.	Treatment-emergent Adverse Events Leading to Infusion Delay/Infusion Not Given by Preferred Term and Treatment – Day 1 Until 1st Infusion of 2nd Dose (Safety Analysis Set)
Table 14-6.3.1.4.	Treatment-emergent Adverse Events Leading to Infusion Delay/Infusion Not Given by Preferred Term and Treatment – Day 1 Through End of Study (Safety Analysis Set)
Table 14-6.4.1.1.	Treatment-emergent Adverse Events with Fatal Outcome by Preferred Term and Treatment – Day 1 Until 1st Infusion of 2nd Dose (Safety Analysis Set)
Table 14-6.4.1.2.	Treatment-emergent Adverse Events with Fatal Outcome by Preferred Term and Treatment – Day 1 Through End of Study (Safety Analysis Set)
Table 14-6.4.2.1.	Serious Treatment-emergent Adverse Events by System Organ Class, Preferred Term, Maximum CTCAE Grade and Treatment – Day 1 Until 1st Infusion of 2nd Dose (Safety Analysis Set)
Table 14-6.4.2.2.	Serious Treatment-emergent Adverse Events by System Organ Class, Preferred Term, Maximum CTCAE Grade and Treatment – Day 1 Through End of Study (Safety Analysis Set)
Table 14-6.4.3.1.	Serious Treatment-emergent Adverse Events by Preferred Term and Treatment – Day 1 Until 1st Infusion of 2nd Dose (Safety Analysis Set)
Table 14-6.4.3.2.	Serious Treatment-emergent Adverse Events by Preferred Term and Treatment – Day 1 Through End of Study (Safety Analysis Set)
Table 14-6.5.1.1.	Overall Events of Interest Treatment-emergent Adverse Events by Treatment – Day 1 Until 1st Infusion of 2nd Dose (Safety Analysis Set)
Table 14-6.5.1.2.	Overall Events of Interest Treatment-emergent Adverse Events by Treatment – Day 1 Through End of Study (Safety Analysis Set)
Table 14-6.6.1.1.	Infusion Reactions Including Hypersensitivity Treatment-emergent Adverse Events by Preferred Term – Day 1 Until 1st Infusion of 2nd Dose (Safety Analysis Set)
Table 14-6.6.1.2.	Infusion Reactions Including Hypersensitivity Treatment-emergent Adverse Events by Preferred Term – Day 1 Through End of Study (Safety Analysis Set)
Table 14-6.6.1.2.1.	Cardiac Disorders Treatment-emergent Adverse Events by Preferred Term – Day 1 Until 1st Infusion of 2nd Dose (Safety Analysis Set)

Sponsor: Amgen Inc.

Statistical Analysis Plan

Protocol No: 20130108

10-December-2018/ Version 2.0

Table 14- 6.6.1.2.2.	Cardiac Disorders Treatment-emergent Adverse Events by Preferred Term – Day 1 Through End of Study (Safety Analysis Set)
Table 14- 6.6.1.3.1.	Serious Infections Treatment-emergent Adverse Events by Preferred Term – Day 1 Until 1st Infusion of 2nd Dose (Safety Analysis Set)
Table 14- 6.6.1.3.2.	Serious Infections Treatment-emergent Adverse Events by Preferred Term – Day 1 Through End of Study (Safety Analysis Set)
Table 14- 6.6.1.4.1.	Progressive Multifocal Leukoencephalopathy Treatment-emergent Adverse Events by Preferred Term – Day 1 Until 1st Infusion of 2nd Dose (Safety Analysis Set)
Table 14- 6.6.1.4.2.	Progressive Multifocal Leukoencephalopathy Treatment-emergent Adverse Events by Preferred Term – Day 1 Through End of Study (Safety Analysis Set)
Table 14- 6.6.1.5.1.	Hematological Reactions Treatment-emergent Adverse Events by Preferred Term – Day 1 Until 1st Infusion of 2nd Dose (Safety Analysis Set)
Table 14- 6.6.1.5.2.	Hematological Reactions Treatment-emergent Adverse Events by Preferred Term – Day 1 Through End of Study (Safety Analysis Set)
Table 14- 6.6.1.6.1.	Hepatitis B Reactions Treatment-emergent Adverse Events by Preferred Term – Day 1 Until 1st Infusion of 2nd Dose (Safety Analysis Set)
Table 14- 6.6.1.6.2.	Hepatitis B Reactions Treatment-emergent Adverse Events by Preferred Term – Day 1 Through End of Study (Safety Analysis Set)
Table 14- 6.6.1.7.1.	Opportunistic infections Treatment-emergent Adverse Events by Preferred Term – Day 1 Until 1st Infusion of 2nd Dose (Safety Analysis Set)
Table 14- 6.6.1.7.2.	Opportunistic infections Treatment-emergent Adverse Events by Preferred Term – Day 1 Through End of Study (Safety Analysis Set)
Table 14- 6.6.1.8.1.	Hypogammaglobulinemia Treatment-emergent Adverse Events by Preferred Term – Day 1 Until 1st Infusion of 2nd Dose (Safety Analysis Set)
Table 14- 6.6.1.8.2.	Hypogammaglobulinemia Treatment-emergent Adverse Events by Preferred Term – Day 1 Through End of Study (Safety Analysis Set)

Sponsor: Amgen Inc.

Statistical Analysis Plan

Protocol No: 20130108

10-December-2018/ Version 2.0

Table 14-6.6.1.9.1.	Severe Mucocutaneous Reactions Treatment-emergent Adverse Events by Preferred Term – Day 1 Until 1st Infusion of 2nd Dose (Safety Analysis Set)
Table 14-6.6.1.9.2.	Severe Mucocutaneous Reactions Treatment-emergent Adverse Events by Preferred Term – Day 1 Through End of Study (Safety Analysis Set)
Table 14-6.6.1.10.1.	Gastrointestinal Perforation Treatment-emergent Adverse Events by Preferred Term – Day 1 Until 1st Infusion of 2nd Dose (Safety Analysis Set)
Table 14-6.6.1.10.2.	Gastrointestinal Perforation Treatment-emergent Adverse Events by Preferred Term – Day 1 Through End of Study (Safety Analysis Set)
Table 14-6.6.2.1.1.	Infusion Reactions Including Hypersensitivity Treatment-emergent Adverse Events by Preferred Term, Maximum CTCAE Grade, and Treatment – Day 1 Until 1st Infusion of 2nd Dose (Safety Analysis Set)
Table 14-6.6.2.1.2.	Infusion Reactions Including Hypersensitivity Treatment-emergent Adverse Events by Preferred Term, Maximum CTCAE, and Treatment – Day 1 Through End of Study (Safety Analysis Set)
Table 14-6.6.2.2.1.	Infusion Reactions Including Hypersensitivity Treatment-emergent Adverse Events of Interest (EOI) by Infusion, Preferred Term, and Treatment – Day 1 Through End of Study (Safety Analysis Set)
Table 14-6.7.1.	Exposure Adjusted Incidence Rate for Treatment-emergent Adverse Events by Preferred Term and Treatment - Day 1 Through End of Study (Safety Analysis Set)
